**(NCT03860662)**

**Study Protocol and Statistical Analysis Plan**

A total of 29 patients who developed spastic hemiplegia as a result of embolism or hemorrhage with Modified Ashworth Scale (MAS) phases of 2-4 and applied to Hatay Mustafa Kemal University, Faculty of Medicine, Physical Medicine and Rehabilitation polyclinic between the dates May 2018 – March 2019 were included in the study. Randomization was performed by generating random numbers as the Group 1 and Group 2. 15 patients were included in Group 1 to receive Botulinum toxin treatment, whereas 14 patients were included in Group 2 to receive Baclofen treatment.

Individuals who had received botulinum toxin injection treatment in the past 6 months, patients receiving oral antispastic treatment, individuals who have an allergy and hypersensitivity story related to the medication to be used, individuals who had diseases that might cause neuropathy and/or used medication and substances which might cause neuropathy in their medical history, individuals with hematoma, infections or skin lesions in the planned injection area, hemorrhage disorders, joint contracture and patients who were MAS grade were excluded from the study. Our study was regarded as positive and approved by decision 2018/159 of Hatay Mustafa Kemal University, Tayfur Ata Sökmen Faculty of Medicine, Clinical Researches Ethics Committee. Informed consent form was taken from all the participants of the study. The study was carried out in accordance with the Helsinki Declaration. The Clinical Trial number is NCT03860662.

The patients' gender, age, weight, height, cerebrovascular case etiology, symptom durations and hemiplegic sides were recorded. MAS was used to evaluate spasticity intensity. MAS grading is done as 1,1+,2,3,4 and it was graded successively as 1,2,3,4,5 to be able to do statistical analysis. The motor evaluation of the patients was performed using Brunnstrom motor staging (upper extremity, hand, lower extremity). A 10 cm. long Visual Analogue Scale (VAS) was used to evaluate the hemiplegic side pain of the patients. The daily life activities of the patients were evaluated with the Barthel index. The Barthel index consists of 10 questions and the highest total score that can be received is 100 (0-20 points: total dependency;

21-61 points: severe dependency; 62-90 points: moderate dependency; 91-99 points: slight dependency; 100 points: total independence). The nociceptive flexor reflex (NFR) threshold value measurement was performed with electromyography on the unaffected lower extremities of the patients. The electrical stimulations were given with a bipolar stimulator from the sural nerve, near side of the lateral malleolus. In order to achieve a threshold value, the electrical stimulation was started from 0mA and increased in intervals (4mA intervals) until a NFR response was achieved. After the initial NFR response was achieved, the stimulation intensity was decreased in 2mA intervals until the response disappeared. Then, the stimulation intensity was arranged with high and low stimulations of 1mA until a stable NFR response was achieved. The stable NFR threshold value achieved in this manner was recorded. The electrical stimulation intensity which made it possible for the NFR threshold response to be achieved was recorded as mA unit. Prior to the treatment and on the 6th week which was the end of treatment, MAS, Brunnstrom stages, VAS values, Barthel daily life activities index and electromyographic NFR thresholds of all patients were recorded.

The 15 patients in the first group were injected onabotulinumtoxin A under ultrasonography guidance in their upper and lower extremity muscles which were 2 and over according to MAS, in suitable dosages according to the pre-determined dosage diagram (total dosage 100-300 IU). The 14 patients in the second group were given 5 mg of oral baclofen twice daily as the initial dosage starting from the first day. This was increased 5mg every 5 to 7 days up to 80mg until the effective antispasticity dosage was achieved (total dosage 30-80 mg). The dosage was not increased anymore since the patients were not able to tolerate higher dosages. Both patient groups were applied a physical therapy and rehabilitation program together with antispastic treatment. In the rehabilitation procedure, positioning, joint range of motion and stretching exercises, strengthening exercises, balance and coordination, ambulation exercises, hot or cold compress, functional electrical stimulation treatments were applied to each patient for 60 minutes. The treatment program was applied by the same physiotherapist for 6 weeks, 5 times a week and once each day.

All obtained data were recorded with the Statistical Package Social Sciences (SPSS) version 21.0 statistical software. The control and analyses of the data were performed with the same software. In the statistical analyses, frequency (%) (median – minimum and maximum) was used for descriptive statistics. The mean and standard deviation values were expressed as ( $m \pm SD$ ). The data obtained through the measurements were evaluated separately each group with ShapiroWilk test in terms of normal distribution. In the comparison of values

which did not display normal distribution, nonparametric tests were used. While Mann-Whitney U test was used in the comparison of the two groups, Wilcoxon Signed Ranks test was used within the same group prior to and after comparisons. In the statistical analyses, p values lower than 0,05 were accepted as significant.

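### Symptom duration is recorded but not used in the between-arm comparison; adjusting for it could recover some precision and correct a chance imbalance in a 15 versus 14 trial

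*Combined protocol and SAP*

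**What the plan says.** All references are to the combined protocol and SAP, which has a single heading and unnumbered paragraphs.

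- **Entry.** The opening paragraph takes patients with spastic hemiplegia "as a result of embolism or hemorrhage with Modified Ashworth Scale (MAS) phases of 2-4". Neither it nor the exclusion paragraph gives a minimum or maximum time since stroke. The only time window concerns prior treatment: "Individuals who had received botulinum toxin injection treatment in the past 6 months".
- **Allocation.** "Randomization was performed by generating random numbers as the Group 1 and Group 2". No stratification factor is named, and nothing is said about blocking. The result was 15 patients on botulinum toxin and 14 on baclofen.
- **Recorded characteristics.** The paragraph on assessments says that "cerebrovascular case etiology, symptom durations and hemiplegic sides were recorded". The term for duration is not defined; here it is taken to mean time since onset.
- **Outcomes.** MAS, Brunnstrom stages, VAS pain, Barthel index and the NFR threshold are measured "Prior to the treatment and on the 6th week which was the end of treatment". Both arms receive rehabilitation throughout.
- **Analysis.** The final paragraph says that "Mann-Whitney U test was used in the comparison of the two groups". It names no covariate, stratified test or model, and does not say whether the test is applied to week-6 values or to changes.

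**The concern.** Motor stage, daily function and spasticity can change over six weeks of rehabilitation without any drug effect, and the amount may depend on how recently the stroke occurred. Two patients with the same baseline Barthel score can have different expected change under identical care if one is still recovering and the other has reached a plateau. The baseline score does not carry that difference; symptom duration can.

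Two things are at stake in a trial of 29. First, recovery-related spread that a covariate could explain stays in the error of the drug comparison and lowers power. Second, if more early patients happen to fall in one arm, the observed difference shifts towards that arm, and the planned test has no means of correcting it.

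**Working it through.** The plan gives no power, effect size or SD, so there is no figure of its own to reproduce.

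**Inputs from the document:** 29 patients, 15 versus 14; significance at 0.05 (two-sided assumed); Mann-Whitney U test between arms.

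**Assumptions, not in the document:** 30-50% of patients are early after stroke (9 to 14 of 29). They gain g = 0, 0.5, 1 or 1.5 residual SD more over six weeks than the others. The true drug difference is 0 or 1 residual SD. Outcomes are continuous.

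**1. How often the arms differ in early patients.** With K early patients of 29, the number falling in the arm of 15 is hypergeometric. The probability that the arms differ by at least 25 percentage points is:
- K = 9: 0.109
- K = 10: 0.245
- K = 12: 0.139
- K = 14: 0.143

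The value at K = 10 is higher because counts are discrete: 7 versus 3 gives 7/15 − 3/14 = 0.252, just over the threshold.

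**2. What such an imbalance does.** A 25-point imbalance moves the expected difference by 0.25 × g, that is 0.125, 0.25 or 0.375 residual SD for g = 0.5, 1 or 1.5. The chance standard error of the difference is √(1/15 + 1/14) = 0.372 SD. In simulation (4,000 trials per setting, 9 or 14 early patients), the Mann-Whitney false-positive rate within the imbalanced trials only is about 6%, 9-10% and 16%. Each rate rests on roughly 4,000 × 0.109 = 436 to 4,000 × 0.143 = 572 trials, so its Monte Carlo standard error can reach √(0.16 × 0.84/436) = 1.8 points. Over all randomisations the rate stays near 5%.

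**3. Power at a true difference of 1 residual SD.**

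| Extra gain g of early patients | Unadjusted Mann-Whitney | Rank ANCOVA, log symptom duration |
|---|---|---|
| 0 | about 70% | about 70% |
| 0.5 SD | 67% | 68-69% |
| 1 SD | 58-63% | 64-68% |
| 1.5 SD | 50-52% | 61% |

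With an early/late covariate split at exactly the true cut-point, power is 68-70% for g from 0.5 to 1.5. That is a ceiling, because the plan gives no cut-point. These runs isolate symptom duration; the baseline value was not in the model.

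**4. Closed-form check of the last row.** With early share p, the unadjusted variance is 1 + g²p(1 − p). At p = 0.5 and g = 1.5 this is 1 + 2.25 × 0.25 = 1.5625, an SD of 1.25. A difference of 1 residual SD is then 1/1.25 = 0.8 total SD. The noncentral t (27 df) gives 54.6% power at 0.8 SD, and simulated Mann-Whitney power at 0.8 SD is about 51-52%, in line with the table. The correlation of early status with outcome is √(0.5625/1.5625) = 0.6. Removing it restores 0.8/√(1 − 0.36) = 1.0 SD, with 73.6% power on 26 df for ordinary ANCOVA, consistent with the rank-based ceiling.

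**5. If duration barely matters.** At correlation 0.1 and a 0.8 SD difference, power is 54.6% unadjusted and 54.9% adjusted, so nothing material is gained or lost.

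**The case against.** The strongest reply is that an unadjusted rank test is valid in a randomised trial. Its p-value already allows for chance imbalance, and the 6-16% false-positive rates come from looking only at badly imbalanced allocations, which could be done for any prognostic factor. This stands. A reader might infer that natural recovery confounds the drug comparison or inflates its overall error rate. The documents do not support that: patients were randomised, and overall type I error stays near 5%.

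The size is wholly assumed, and this also stands. A reader might infer that patients from weeks to years after stroke were in fact mixed. The documents only fail to exclude it. Recruitment through an outpatient clinic, with spasticity already present, makes a mostly later population plausible, and then little is lost.

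Three narrower replies also hold. The text is in the past tense and all 29 patients are allocated, so stratifying the randomisation is no longer available. Nothing in the documents supports a recovery argument for VAS pain or for an NFR threshold measured on the unaffected leg. The document does not say that randomisation was unrestricted; it is silent.

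What does not stand is that adjustment is therefore only a matter of taste. The variable is already collected, one degree of freedom costs almost nothing even when duration is irrelevant, and the possible gain is useful at this sample size.

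**Conclusion.** The concern holds as one of precision and uncorrected chance imbalance, not of validity. Under the stated assumptions, adding log symptom duration changes power from about 70% to about 70% (no extra gain in early patients), from 67% to 68-69% (0.5 SD), from 58-63% to 64-68% (1 SD) and from 50-52% to 61% (1.5 SD). The benefit thus runs from nothing to roughly 10 percentage points.

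The figures rest on an assumed early share of 30-50%, a step-shaped recovery difference, a true drug effect of 1 SD and continuous outcomes. MAS and Brunnstrom stage have few levels, so the figures are illustrative for them. The conclusion also takes the recorded symptom duration to be time since onset. It applies to MAS, Brunnstrom stage and Barthel index only.

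**What to change.** For MAS, Brunnstrom stage and Barthel index, add a between-arm rank ANCOVA or proportional-odds model with treatment, the baseline value and log symptom duration. Define symptom duration as time since onset if that is what was recorded, and report its distribution by arm. If outcome data have already been seen, present the adjusted result as a labelled sensitivity analysis beside the Mann-Whitney result, not in place of it.

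The cost is wording and one further analysis on data already held. Symptom duration uses one degree of freedom and the baseline value another, leaving 25 residual degrees of freedom (29 − 4) in the rank ANCOVA. No change to the randomisation is proposed.

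### Does the MAS coding list, which starts at grade 1, lose patients whose spasticity resolves or blur the entry criterion?

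*Combined protocol and SAP*

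**What the plan says.** The document has one unnumbered section, Study Protocol and Statistical Analysis Plan. Its paragraphs bear on the point as follows.

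- **Outcome measures:** "MAS grading is done as 1,1+,2,3,4 and it was graded successively as 1,2,3,4,5 to be able to do statistical analysis". MAS is the only spasticity measure described.
- **Entry:** patients had spastic hemiplegia "with Modified Ashworth Scale (MAS) phases of 2-4".
- **Exclusions:** the list ends "joint contracture and patients who were MAS grade were excluded from the study". The grade number is absent from the text as supplied, which may be an extraction gap, so nothing is built on it.
- **Timing:** "Prior to the treatment and on the 6th week which was the end of treatment, MAS, Brunnstrom stages, VAS values" and the remaining measures were recorded for all patients.
- **Treatment:** the toxin was injected into "upper and lower extremity muscles which were 2 and over according to MAS".
- **Statistics:** nonparametric tests are used for values that are not normally distributed. "While Mann-Whitney U test was used in the comparison of the two groups", and the Wilcoxon signed ranks test is used within groups.

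The documents do not mention a grade below 1, give no week-6 MAS results, and do not say that any patient was left out of the MAS analysis or rescored.

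**The concern.** Two features invite suspicion.

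First, the drugs under test aim to reduce tone, so a muscle with no increased tone at week 6 is the best possible result, yet the list gives it no number. If such a score were set to missing, the best outcomes would leave the analysis. If it were entered as 1, it would be pooled with grade 1. Either choice would shrink a real advantage for the arm with more complete responses, provided that arm's other patients do no worse. With groups this small, a few patients matter.

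Second, the digits 2, 3 and 4 have different meanings before and after conversion. If the entry range were stated in analysis codes, it would admit grade 1+ and shut out grade 4. If the muscle threshold were stated in codes, it would also take in grade 1+. Neither sentence says outright which set of numbers it uses.

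**Working it through.** The plan gives no figure to reproduce. The check has three parts.

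**1. The mapping.** The rule sends 1→1, 1+→2, 2→3, 3→4, 4→5. The one grade that is not a number is 1+, and giving it a place in the order is what forces renumbering. The value 0 is not assigned to anything. Entering absence of spasticity as 0 therefore preserves the order and alters none of the five listed codes.

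**2. Which numbers the criteria use.**

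| Statement | Read as MAS grades | Read as analysis codes |
|---|---|---|
| Entry 2 to 4 | grades 2, 3, 4 (codes 3, 4, 5) | grades 1+, 2, 3; grade 4 excluded |
| Muscles at 2 or more | grades 2, 3, 4 | grades 1+, 2, 3, 4 |

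The conversion is introduced for statistical analysis only. Both criteria name the MAS itself. The upper entry limit of 4 is the top grade, whereas the top code is 5. Read as grades, the two statements start at the same grade and agree.

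**3. What is at stake if a resolved score is mishandled.** All distributions below are assumed.

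*Mean-code illustration.* Let the patients who do not resolve have proportions 0.25, 0.30, 0.30, 0.10, 0.05 on codes 1 to 5 in both arms.

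- Mean code: 0.25 + 0.60 + 0.90 + 0.40 + 0.25 = 2.4.
- Resolved 20% v 0%: coded 0, the difference is 0.20 × 2.4 = 0.48. Coded 1, it is 0.20 × (2.4 − 1) = 0.28. Dropped, it is 0.
- Resolved 20% v 7%: coded 0, 0.13 × 2.4 = 0.31. Coded 1, 0.13 × 1.4 = 0.18. Dropped, 0.

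Coding as 1 shrinks the mean difference by 1/2.4 = 42%. The zero under dropping is built in, because the remaining patients were given identical distributions.

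*The same illustration on the rank-test scale.* Mann-Whitney reflects P(better) + ½P(tie), less ½.

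- 20% v 0%, coded 0: 0.20 × 1 + 0.80 × 0.5 − 0.5 = 0.100.
- 20% v 0%, coded 1: 0.20 × (0.75 + 0.25/2) + 0.80 × 0.5 − 0.5 = 0.075.
- 20% v 7%: 0.13 × 0.5 = 0.065 coded 0, and 0.13 × 0.375 = 0.049 coded 1.

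On the scale of the named test the shrinkage is 25%, not 42%.

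*Simulated power.* 3,000 replicates per row, 15 v 14 patients, two-sided Mann-Whitney at 0.05. The comparator has proportions 0.10, 0.20, 0.30, 0.25, 0.15 on codes 1 to 5 and no resolved patients. The unresolved part of the other arm has 0.25, 0.30, 0.25, 0.15, 0.05.

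| Resolved share in one arm | Coded 0 | Coded 1 | Dropped |
|---|---|---|---|
| 0% | 0.325 | 0.325 | 0.325 |
| 5% | 0.395 | 0.388 | 0.329 |
| 10% | 0.453 | 0.430 | 0.302 |
| 20% | 0.589 | 0.550 | 0.292 |
| 30% | 0.734 | 0.682 | 0.258 |

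For shares of 5% to 30%, coding as 1 costs 0.395 − 0.388 = 0.007 up to 0.734 − 0.682 = 0.052. Dropping costs 0.395 − 0.329 = 0.066 up to 0.734 − 0.258 = 0.476.

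**The case for a change.** The best case for acting is that the list is written as closed and that a resolved muscle is a foreseeable result of six weeks of antispastic drug plus rehabilitation five times a week. If the true share were 5%, 10% or 20%, the chance of at least one such patient among 15 would be 1 − 0.95^15 = 54%, 1 − 0.90^15 = 79% or 1 − 0.80^15 = 97%. The gap might also reach baseline. Muscles were selected for injection by a threshold, which implies that others scored lower, and the text does not say which muscle or limb score is analysed. The within-group test is touched as well: resolution from codes 3, 4 and 5 is a fall of 3, 4 and 5 if coded 0, of 2, 3 and 4 if coded 1, and no pair at all if dropped.

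Much of this stands. The list is silent on absence of spasticity, and dropping such scores would be harmful. But missing and 1 are not the only options: 0 is open at both visits, for any muscle, and is the obvious entry. Dropping would also leave a trace. At a 20% share, 0.20 × 15 = 3 patients would be absent from the week-6 MAS count. That the scale has a grade for no increased tone is itself an assumption here, since the documents list only 1 to 4 with 1+.

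**Conclusion.** No change to the plan follows. The silence on absence of spasticity is a gap in detail that an analyst fills sensibly by entering 0, and that choice loses nothing in either the Mann-Whitney or the Wilcoxon test. The supposed conflict between codes and entry numbers disappears when the criteria are read as MAS grades, as their wording and the upper limit of 4 suggest. At most a clarifying phrase is missing. Which grades ought to qualify for entry or injection is a clinical matter and is not judged here.

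The size of any effect rests wholly on assumed week-6 distributions. In those scenarios, coding resolved muscles as 1 costs about 1 to 5 percentage points of power, and dropping them costs about 7 to 48. With no such patients the effect is nil. The direction is also conditional: if the arm with more resolved patients did worse otherwise, mishandling could widen a difference the other way. The conclusion would change only with evidence that resolved scores were in fact discarded, and the documents contain none.

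### Entry requires no pain and the between-group VAS test is unadjusted, so any patients starting at VAS 0 would dilute the pain comparison; stratifying by baseline pain recovers part of the loss at no cost in data

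*Combined protocol and SAP*

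**What the plan says.** The combined protocol and SAP has no numbered sections, so places are given by paragraph.

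- **Opening paragraph, study population.** Patients are those who "developed spastic hemiplegia as a result of embolism or hemorrhage with Modified Ashworth Scale (MAS) phases of 2-4". Neither this nor the exclusion list in the next paragraph mentions pain. Arm sizes are given: "15 patients were included in Group 1 to receive Botulinum toxin treatment, whereas 14 patients were included in Group 2 to receive Baclofen treatment".
- **Outcome measures paragraph.** "A 10 cm. long Visual Analogue Scale (VAS) was used to evaluate the hemiplegic side pain of the patients".
- **Assessments.** Before treatment and at week 6, "MAS, Brunnstrom stages, VAS values, Barthel daily life activities index and electromyographic NFR thresholds of all patients were recorded".
- **Final paragraph, statistics.** Nonparametric tests are used for values that are not normally distributed: "While Mann-Whitney U test was used in the comparison of the two groups", with a Wilcoxon signed-ranks test within each group. The threshold is "p values lower than 0,05 were accepted as significant". No other between-group test is named.

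The text does not say whether the Mann-Whitney test is run on week-6 values or on change. It describes no baseline adjustment, no stratification and no separate VAS analysis set. It gives no baseline VAS values, no count of patients at 0, no primary endpoint and no power figure.

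**The concern.** VAS has a floor at 0. A patient who starts there cannot improve under either drug, so that patient's change is 0 (or positive, if new pain appears) whatever the treatment. In an all-patient rank test these patients are a tied block that appears in both arms and carries no information on pain relief, while the difference among patients who do have pain is spread over a larger denominator.

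With 15 and 14 patients there is little power to spare. A VAS result that is not significant could be read as showing no difference between the drugs when part of the sample had no pain to relieve. Without the count at 0 per group, a reader could not tell the two explanations apart.

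**Working it through.** The plan states no VAS power, so there is no figure of its own to reproduce.

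**Inputs from the documents.** 15 v 14 patients; 10 cm VAS; Mann-Whitney U; threshold 0.05 (sidedness not stated, two-sided assumed).

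**Assumed inputs.** In patients with pain: baseline mean 5 cm (SD 2), mean fall 1 cm in one arm and 3 cm in the other, SD of change 1.8 cm. A share f starts at 0 and stays at 0. No dropout.

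**Benchmark.** With every patient in pain, the standardised difference giving 80% power is (1.96 + 0.842) × √(1/15 + 1/14) = 2.802 × 0.3716 = 1.04 SD. The assumed effect is 2/1.8 = 1.11 SD.

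**Hand check of the mechanism** (normal approximation, ignoring the floor for patients in pain).

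For all 29, the mean difference becomes 2(1−f). The variance of change in an arm with mean fall μ becomes (1−f)·1.8² + f(1−f)·μ². At f = 0.2:

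- Variance with μ = 3: 0.8 × 3.24 + 0.16 × 9 = 4.032
- Variance with μ = 1: 0.8 × 3.24 + 0.16 × 1 = 2.752
- SE = √(4.032/15 + 2.752/14) = 0.682
- Power = Φ(1.6/0.682 − 1.96) = Φ(0.385) = 65%

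Setting the pain-free block aside leaves 12 v 11.2 patients and the full 2 cm difference: SE = √(3.24/12 + 3.24/11.2) = 0.748, and power = Φ(2/0.748 − 1.96) = Φ(0.71) = 76%. The same steps for the other shares give:

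| Share at VAS 0 | 0% | 10% | 20% | 40% |
|---|---|---|---|---|
| All 29, unadjusted | 85% | 75% | 65% | 45% |
| Pain-free block set aside | 85% | 81% | 76% | 64% |
| Difference (points) | 0 | 6 | 11 | 19 |

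**Simulation with the scale bounded at 0 and rank tests.** The levels are lower because patients in pain can also hit the floor, but the pattern is the same.

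| Share at VAS 0 (of 29) | 0% (0) | 10% (about 3) | 20% (about 6) | 40% (about 12) |
|---|---|---|---|---|
| Mann-Whitney, week-6 values | 46% | 34% | 26% | 13% |
| Mann-Whitney, change | 74% | 63% | 51% | 31% |
| Baseline-adjusted ranks, all 29 | 73% | 67% | 62% | 46% |
| Van Elteren on change, stratified by baseline pain | 74% | 69% | 63% | 49% |

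Type I error is about 4-6%. On change, the loss against 0% pain-free is 74−63 = 11, 74−51 = 23 and 74−31 = 43 points. Stratifying recovers 69−63 = 6, 63−51 = 12 and 49−31 = 18 of these. The rest is lost because fewer patients have pain.

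The stratified statistic is Σ[W − E(W)]/(N+1) divided by √ΣVar(W)/(N+1)², summed over the two baseline strata, with W the rank sum in one arm and N the stratum size. If nobody starts at 0 there is one stratum, and this is the ordinary Mann-Whitney test.

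**Sensitivity.**

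- With the effect set to give 80% power when all have pain, SD of improvement 2 cm and other baselines and mean falls, power on change becomes 62-73% at 10% pain-free, 45-65% at 20% and 31-55% at 30%. On week-6 values it becomes 59-66%, 41-55% and 27-42%.
- With an extra fall of 1 cm instead of 2, power is about 27% with everyone in pain, and stratifying gains about 2-4 points.

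**The case against.** **The loss is not shown to have happened.** A reader might infer that patients at VAS 0 were enrolled and cost the comparison much of its power. The documents do not support that: they report no baseline VAS and no count at 0. That all 29 enter the VAS test is itself a fair inference from VAS being recorded in all patients, not an explicit statement. This objection stands, and it makes the point conditional.

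**Another gap is larger under these assumptions.** With no pain-free patients at all, testing week-6 values instead of change takes power from 74% to 46%, a difference of 28 points. The plan leaves that choice open. This stands, and the fix must settle it too.

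**Ordinary baseline adjustment nearly suffices.** A reader might infer that adjusting for baseline cannot repair the dilution. Up to 40% pain-free, baseline-adjusted ranks in all 29 are within 1-3 points of the stratified test. The gap widens if pain-free patients develop new pain: at 40% pain-free with 10% of them reporting new pain, power is about 37% for adjusted ranks and 42-43% for the stratified test. Adjustment is a reasonable alternative.

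**Restriction changes the question.** It is tempting to make patients with baseline VAS above 0 the main comparison. In that same new-pain setting restriction reaches 48-49%, but only by leaving new pain, a real outcome, out of the test. It also moves the target from patients with spastic hemiplegia to those who also have pain. Without new pain it has no material advantage over stratifying.

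**Small size and status.** No outcome is named primary, and 15 v 14 is small for anything below about 1 SD. Both are true. They limit the importance of the point, not its direction.

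**Conclusion.** The point holds in conditional form. The plan admits patients with no pain, records VAS in all patients, and names only an unadjusted Mann-Whitney U for the between-group comparison. Any patients starting at 0 would dilute that comparison.

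Under the stated assumptions the loss on change is about 11 points at 10% pain-free, 23 at 20% and 43 at 40%. Stratification recovers about 6, 12 and 18 of these. The loss from this source is nil if every patient has pain, and the recoverable part is only a few points if the true extra fall is 1 cm. Type I error is not the issue: the risk is a missed difference and a null result that cannot be interpreted.

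All of these sizes depend on the assumed effect, SD and share at 0, none of which the documents give.

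**What to change.** Add to the statistical paragraph, in substance: the between-group comparison of VAS uses change from baseline to week 6 in all randomised patients, by a van Elteren test stratified by baseline pain (VAS 0 versus above 0). The number with baseline VAS 0, and the number of those with new pain at week 6, are reported per group. The comparison restricted to baseline VAS above 0 is a supporting analysis only.

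This fixes the analysed variable, keeps every randomised patient, and splits on a pre-treatment value only. It needs no further patients and no further measurements, because baseline VAS is already recorded. The cost is a few sentences and one slightly less familiar test; if the named software has no routine for it, the statistic can be computed from the two within-stratum rank sums. The document is written in the past tense, so if outcome data had already been seen when the wording was added, the analysis should be labelled post hoc.

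### Can the stated baclofen titration reach the top of its 30-80 mg range within the six-week treatment period?

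*Combined protocol and SAP*

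**What the plan says.** All the relevant text is in the unnumbered section Study Protocol and Statistical Analysis Plan of the combined document.

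- **Start.** The 14 patients in Group 2 were "given 5 mg of oral baclofen twice daily as the initial dosage starting from the first day", which is 10 mg/day.
- **Titration.** "This was increased 5mg every 5 to 7 days up to 80mg until the effective antispasticity dosage was achieved (total dosage 30-80 mg".
- **Stopping.** Besides the effective dose just mentioned, the next sentence gives a second reason: "The dosage was not increased anymore since the patients were not able to tolerate higher dosages".
- **Assessment.** All outcomes were recorded "Prior to the treatment and on the 6th week which was the end of treatment".
- **Toxin arm.** The range for the other group is written in the same style: "in suitable dosages according to the pre-determined dosage diagram (total dosage 100-300 IU".
- **Analysis.** The closing paragraph names the Mann-Whitney U test between groups and the Wilcoxon signed ranks test within groups. For summaries, "frequency (%) (median – minimum and maximum) was used for descriptive statistics".

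The text does not say whether the 5 mg step is added to the daily total or to each dose, or whether 30-80 mg is a permitted or an achieved range.

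**The concern.** The step and the ceiling stand in one sentence, and the range is called a total. It is natural to read both as daily amounts. Going from 10 to 80 mg/day in 5 mg steps then takes 14 steps. At one step every 5 to 7 days that is 70 to 98 days of titration, against a treatment period of 42 days.

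Baclofen is the only comparator, in 14 patients, with a single post-treatment assessment. If the upper part of the range could not be reached by then, a reader might think the toxin was compared with a baclofen arm still being titrated, or with a lower dose than the text suggests. A dose reached only just before the assessment would raise the same doubt. The two stopping reasons add to it: a patient who stopped at an effective dose and one who stopped through intolerance represent different comparators, and no counts are given.

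**Working it through.** **Inputs.** Starting dose 2 x 5 = 10 mg/day on day 1. Step 5 mg every k = 5, 6 or 7 days. Range 30-80 mg, taken as a daily dose; as a cumulative amount, 80 mg would be used up in 80/10 = 8 days at the starting dose alone. Assessment on day 42 (an assumption for week 6). Twice-daily dosing is assumed to continue.

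**Formula.** Steps completed by day 42: n = floor((42 - 1)/k), which gives 8, 6 and 5. Highest dose = 10 + s x n, capped at 80, where s is the rise in the daily total per step. A dose D is reached on day 1 + k x (D - 10)/s.

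| Step basis | k (days) | n | Highest dose by day 42 | 30 mg/day reached | 80 mg/day reached |
|---|---|---|---|---|---|
| Daily total, s = 5 | 5 | 8 | 10 + 40 = 50 | day 21 | day 71 |
| Daily total, s = 5 | 6 | 6 | 10 + 30 = 40 | day 25 | day 85 |
| Daily total, s = 5 | 7 | 5 | 10 + 25 = 35 | day 29 | day 99 |
| Each of two doses, s = 10 | 5 | 8 | 10 + 80 = 90, capped at 80 | day 11 | day 36 |
| Each of two doses, s = 10 | 6 | 6 | 10 + 60 = 70 | day 13 | day 43 |
| Each of two doses, s = 10 | 7 | 5 | 10 + 50 = 60 | day 15 | day 50 |

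**Can the stated 80 mg be reproduced?** Not on the daily-total reading, where 50 mg/day is the most that fits and is reached only on day 41. On the per-dose reading it can be reached: 80 mg/day needs (80 - 10)/10 = 7 steps, which fit if the average interval is at most 41/7 = 5.86 days.

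**Sensitivity to the day count.** Extending the last day to 43, which is the same as counting the first dose as day 0 and including a step on day 42, gives 50, 45 and 40 mg/day on the daily total and 80, 80 and 70 mg/day per dose. An assessment early in week 6, on day 36, gives n = floor(35/k) = 7, 5, 5, hence 45, 35, 35 and 80, 60, 60 mg/day. The 50 mg/day limit on the daily-total reading holds throughout; the other figures move by one step.

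**Which readings conflict?**

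| | 30-80 mg permitted | 30-80 mg achieved |
|---|---|---|
| Step on the daily total | No conflict: a ceiling need not be reached | Conflict above 50 mg/day |
| Step on each dose | No conflict | No conflict at intervals averaging 5.86 days or less |

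The lower end, 30 mg/day, is reached by day 29 at the latest on either step basis.

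**Does dose enter the analysis?** No. The between-group and within-group tests use outcome values and group membership only. Settling the step basis would leave every test statistic and p value unchanged.

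**The case for a change.** The strongest case for acting is that the comparator is not pinned down. Depending on an unstated convention, the schedule allows at most 35-50 or 60-80 mg/day at week 6, so another site could not reproduce the arm from this text. If the range was only permitted and the step was on the daily total, the range would include doses that could not occur within the trial. The intolerance sentence suggests that titration had ended, but gives no dose, date or count. Clarifying the wording and summarising the doses of 14 patients would cost little.

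Most of that is true as a remark on description. It does not show a fault in the plan. The per-dose reading is at least as open as the other, because the sentence on increases follows directly on a twice-daily dose of 5 mg. A permitted range with an unreachable upper part would be redundant, but not contradictory. Titration to effect, limited by tolerance, means that no single comparator dose was ever intended; the comparison is between two strategies. Nothing in the text shows that patients were still escalating at week 6. The dose each patient reached and the reason for stopping are results, and the descriptive format already stated can carry them if dosing records exist. What stands is that any account of the findings should not attribute a particular baclofen dose to the comparison without those data.

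**Conclusion.** No change to the plan follows. The titration text is incomplete on two points, but it is not shown to be wrong: one of four readings conflicts with the six-week period, and the documents do not establish that reading. If the sponsor did mean a daily-total step and an achieved range, the step, interval, range and treatment period would contradict one another and would have to be reconciled. No view is taken here on which dose or schedule is right.

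The gap leaves the schedule's maximum at week 6 anywhere from 35 to 80 mg/day across the readings, with an exact limit of 50 mg/day on the daily-total reading. This rests on a first dose on day 1, assessment by day 42, continued twice-daily dosing and no interval shorter than 5 days. The randomised comparison of strategies and the planned tests are unaffected. Writing down the convention would help a reader describe the comparator, but it would alter no estimate, test or conclusion about which group did better.
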